Upon informed consent, subjects will undergo physical examination, medical history assessment, vital sign measurements, and x-rays of the injured and/or contralateral ankle as part of their standard clinical care. After initial evaluation, subjects will undergo aspiration of the injured ankle joint via the standard anteromedial arthroscopy portal approach. This will be performed with sterile technique using a 16-gauge needle attached to a 10cc syringe. As previously mentioned, this standard of care needle insertion is used independent of the current study for the administration of intra-articular lidocaine for patient pain relief. The aspirate will be immediately transported to [name] lab (LSRC Building, Room B331) aliquoted and stored at -80 degrees Celsius for batch analysis.

Subjects in Group 1 will then undergo saline joint lavage as follows:

Three 10cc syringes will be filled with 10cc of sterile 0.9% normal saline.

One 10cc normal saline syringe will be injected into the ankle joint through the previously placed anteromedial 16-gauge needle.

Saline will be withdrawn from the joint into the attached 10cc syringe.

The needle will be left in place, the syringe detached, and the lavage repeated with the remaining two 10cc normal saline syringes.

After three rounds of lavage, 10cc of 1% lidocaine without epinephrine will be injected into the joint via the existing anteromedial 16-gauge needle. This will serve as an intra-articular hematoma block for patient comfort during fracture reduction and splinting.

This intra-articular lidocaine block is routinely performed as standard of care for ankle fractures presenting to the emergency department. As described, only one needle stick will be performed which will facilitate sample aspiration, lavage and lidocaine block, thus causing minimal to no additional discomfort to the patient.

Subjects in group 2 will not undergo normal saline lavage. After synovial fluid aspiration as described above, they will undergo intra-articular injection of 10cc of 1% lidocaine without epinephrine via the existing anteromedial 16-gauge needle. This will serve as an intra-articular hematoma block for patient comfort during fracture reduction and splinting.

The aspiration and lavage protocol as described above will take place in the DUH ED and be performed only by approved key study personnel.

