As described above, this study represents minimal risk and discomfort to subjects. It is standard of care to administer an intra-articular lidocaine injection during the emergency department management of ankle fractures. We will utilize this standard of care needle insertion to the fractured ankle to perform our study related aspiration and saline lavage. In this way, no additional risk or discomfort will be incurred by the subject as a result of participation. Patients choosing not to participate will receive the normal standard of care for treatment of their injury independent of this study. Furthermore, consenting to participate in this study in no way obligates subjects to undergo surgical fixation of their ankle fracture. This decision will be made in consultation with their treating surgeon.

Risk is involved to the extent that privacy and confidentiality may be compromised. However, every reasonable effort will be made to limit breaches of privacy and confidentiality.

Subjects will not benefit directly from this study. However, data and conclusions derived from this study may improve the current understanding of post traumatic arthritis and possibly influence future patient care or study designs.

Data Analysis & Statistical Considerations

Sample Size Estimate

The study was powered (a-priori) for randomized between group differences in the primary outcome measures of Cytokines and Matrix Metalloproteinase levels collected during standardized aspirations. The study will involve two independent groups: 1) individuals with intra-articular fractures of the ankle who receive saline lavage (experimental) and 2) individuals with intra-articular fractures of the ankle who do not receive lavage (control). Differences between groups will be evaluated with a fixed effects repeated measures, analysis of covariance (RM-ANCOVA) with three dedicated time points ([1.] baseline, [2.] in the OR after anesthesia is induced (generally within 24 hours of lavage), and [3] 1 to 2 weeks post-injury). Baseline cytokines and Matrix Metalloproteinase levels will be used as a covariate control. Assuming a normal distribution for the cytokines and Matrix Metalloproteinase levels and assuming a partial theta squared effect size of 0.40 (large effect*, primarily occurring at the second time

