point), we constructed a sample size estimation estimating for between groups' comparisons. With an expected 80% power, 2 time intervals*, 1 control interval, two independent groups, and a standard error of probability of 0.05, we estimated the need for a minimum sample size of 40 for statistical significance (~20 per group). We will employ intention to treat and chains equation imputation and will not oversample each group for drop outs.

Statistical Analyses

The primary outcome measure will be cytokines and Matrix Metalloproteinase levels measured at two distinct time points after injury. We will use a between groups, repeated measures Analysis of Covariance (RM-ANCOVA) to measure differences between the two designated groups. A RM-ANCOVA is used in examining the differences in the mean values of the dependent variables that are related to the effect of the controlled independent variables while taking into account the influence of the uncontrolled independent variables (baseline) over more than one time point. A p value of 0.05 will be used to measure statistical significance.

*Medium effect size required a sample size of 98

+Three time intervals would only require a sample size of 36.

Data & Safety Monitoring

The only major risk involved is the loss of confidentiality and every effort will be made to ensure this does not happen by the research staff. No followup contact with subjects will be necessary after their ankle aspirations. The results of this research will not be placed in their medical record. No PHI will leave Duke. It will not be necessary to specifically provide the subjects with any additional information, as their involvement ends with their ankle joint aspiration at the time of surgery and does not influence their longitudinal care. Furthermore, any research findings will be made available through publication. Research records containing MRN will be kept in an electronic spreadsheet on the Duke server of which access is limited to the PI and his research staff. Any electronic information will be stored on a computer that is password protected. After data collection and prior to statistical analysis, a case number will be assigned to the data and the medical record number (the only identifying data collected) will be stripped from the database. After the review is complete, publication has been accepted and all revisions have been made to the manuscript, then the study will be closed in the eIRB.

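### Baseline is listed both as an RM-ANCOVA time point and as the covariate; if entered as an outcome, it shrinks the reported group difference to 2/3 or 1/2 of the post-lavage effect, with the test unchanged

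*Combined protocol and SAP*

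**What the plan says.** All references are to the Combined protocol and SAP.

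- **Sample Size Estimate, design sentence.** Group differences are to be tested by a repeated-measures "analysis of covariance (RM-ANCOVA) with three dedicated time points ([1.] baseline", followed by a sample in the operating room and one at 1 to 2 weeks after injury.
- **Sample Size Estimate, next sentence.** "Baseline cytokines and Matrix Metalloproteinase levels will be used as a covariate control".
- **Sample Size Estimate, calculation.** "With an expected 80% power, 2 time intervals*, 1 control interval, two independent groups", giving a minimum of 40 subjects. Footnotes give 98 for a medium effect and 36 for three time intervals.
- **Statistical Analyses.** "The primary outcome measure will be cytokines and Matrix Metalloproteinase levels measured at two distinct time points after injury". The section then describes the model as accounting for "the influence of the uncontrolled independent variables (baseline) over more than one time point".
- **Design & Procedures.** "After initial evaluation, subjects will undergo aspiration of the injured ankle joint via the standard anteromedial arthroscopy portal approach". Lavage in Group 1 comes after this aspirate. The only other aspiration described is at surgery.
- **Selection of Subjects.** Subjects present within 48 hours of injury, so the ED aspirate is after injury and before lavage.

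No section says whether the tested term is the group main effect, the group-by-time interaction or a contrast at one visit.

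**The concern.** The same measurement is given two roles: one of the repeated responses, and the covariate that adjusts those responses. Because the ED sample precedes lavage, lavage cannot have affected it. If it is among the outcomes and the group main effect is reported, the estimate averages the post-lavage difference with a term that is zero by construction.

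The outcome definition in Statistical Analyses does not settle the matter, because it is anchored to injury and not to the ED procedure. Only two aspirations are described in Design & Procedures, one in the ED and one at surgery. Someone looking for two samples after injury could take exactly those two.

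At stake is the size of the published lavage effect. A figure reduced to two thirds or one half would mislead readers and anyone using it to plan a later trial, a use that the Risk/Benefit Assessment anticipates.

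**Working it through.** **Step 1: reproduce the plan's sample size.** From the plan: effect size 0.40, alpha 0.05, power 80%, two groups, two time intervals. Assumed: correlation ρ = 0.5 between repeated measures, since the documents give none. For the between-groups F test with *m* repeated outcomes,

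λ = f² · N · m / (1 + (m − 1)ρ), with 1 and N − 2 degrees of freedom.

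| f | m | N | λ | Power |
|---|---|---|---|---|
| 0.40 | 2 | 40 | 0.16 × 40 × 2 / 1.5 = 8.53 | 0.812 |
| 0.25 | 2 | 98 | 0.0625 × 98 × 2 / 1.5 = 8.17 | 0.808 |
| 0.40 | 3 | 36 | 0.16 × 36 × 3 / 2 = 8.64 | 0.815 |

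These are the smallest even totals reaching 80%, and all three match the stated 40, 98 and 36. For f = 0.40 and m = 2, the required N is 34 at ρ = 0.3, 44 at ρ = 0.7 and 48 at ρ = 0.8. The match needs 0.40 to be Cohen's f; read literally as a partial eta squared it is f = √(0.4/0.6) = 0.816, and N is about 12.

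Two things follow. The adopted 40 uses two outcomes, so the sizing did not count baseline as a third. And the figures are those of a between-groups main-effect test, which averages over whatever time points are entered.

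**Step 2: what happens if baseline is entered as an outcome.** Let Y0 be the ED value and Y1, Y2 the later values, with baseline-adjusted group differences d1 and d2. Least-squares coefficients are linear in the response, and regressing Y0 on group and Y0 gives a group coefficient of exactly 0.

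- Baseline plus two later samples: (0 + d1 + d2)/3, against (d1 + d2)/2 for the later samples alone. Ratio (1/3)/(1/2) = 2/3.
- Baseline plus the surgery sample: (0 + d1)/2, against d1. Ratio 1/2.

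Y0 adds nothing to the residual either, so the standard error shrinks by the same factor and the t statistic is unchanged.

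**Step 3: simulation.** 20 per group, 4000 runs; SD 1, ρ = 0.5 and a true difference of 0.8 SD are assumptions. Both analyses adjust for baseline.

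| Effect pattern | Estimate, baseline among outcomes | Estimate, later samples only | Power, each |
|---|---|---|---|
| 0.8 at both later samples | 0.53 | 0.80 | 0.93 |
| 0.8 at the first later sample, 0 at the second | 0.27 | 0.40 | 0.41 |
| One later sample, 0.8 | 0.40 | 0.80 | 0.81 |

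The t statistics from the two analyses agreed to about 1e-14 in every run.

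**The case against.** The strongest defence is that the plan gives baseline the covariate role three times: in the sentence after the list, in the control-interval phrase of the calculation, and in Statistical Analyses. The reproduced figures agree with two outcomes. On this view the three time points are simply two outcomes and one control, and the list is loosely worded. The plan also nowhere says that the lavage effect is a mean over all three times. It expects the effect mainly at the second one ("assuming a partial theta squared effect size of 0.40 (large effect*, primarily occurring at the second time" point), and an interaction or single-visit contrast would not be diluted.

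Most of this stands. Covariate-only is the likelier intention, so the plan cannot be said to average the effect over a pre-lavage sample as it is written. But the defence does not remove the ambiguity. The list still names baseline as a time point of the model, the outcome wording still admits the ED aspirate, no tested term is named, and the sizing is that of a main effect.

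Two stronger readings are tempting.

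- **A general understatement of one third to one half.** The two fractions belong to different sampling schemes. The 2/3 factor goes with the three time points in Sample Size Estimate; the 1/2 factor goes with the two aspirations in Design & Procedures. Neither applies unless baseline is entered as an outcome and the main effect is reported.
- **A conservative test and lost power.** In the between-subjects test with baseline as covariate, neither occurs. Power falls if the covariate is dropped while baseline stays an outcome (0.29 against 0.81 with one later sample), but the plan keeps the covariate. A pooled regression with one residual variance and one common baseline slope is also conservative (type I error 2.7%, 3.6% and 4.1% at correlations 0.3, 0.5 and 0.7). That comes from forcing one slope on both times: with baseline-by-time and group-by-time terms added, it is 5.7%, 5.7% and 5.5%. The plan does not specify the pooled model.

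**Conclusion.** The point holds as a conditional one. The documents give baseline two roles and define the outcome in words that can include the pre-lavage ED aspirate. If baseline is analysed as an outcome, as the list of time points has it, the reported main effect is exactly 2/3 of the post-lavage average with two later samples, or 1/2 of the post-lavage effect with the surgery sample alone. These factors are algebraic and depend on no assumed correlation or SD; they require only that baseline is also the covariate and that the group main effect is the reported quantity. The t statistic, p-value and power are unaffected, so the trial's test against the planned threshold ("A p value of 0.05 will be used to measure statistical significance") is not in question. That the stated 40, 98 and 36 match rests on an assumed correlation of 0.5. The fault should be corrected because it bears on the primary estimate and costs nothing to remove.

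**What to change.** 1. In Sample Size Estimate, remove baseline from the outcome time points of the RM-ANCOVA.
2. In Statistical Analyses, define the outcome as the aspirate(s) collected after the ED procedure in both groups. Anchoring to the ED procedure also covers Group 2, which has no lavage. Reconcile the number and timing of these aspirates with Design & Procedures.
3. State in both sections that the ED aspirate enters the model once, as the covariate.
4. Name the baseline-adjusted group difference on the post-ED aspirate(s) as the primary estimate.

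The cost is wording only, with no added samples or patients. With two post-ED aspirates the stated 40 stands, because that is the model behind it. If the reconciliation leaves only one, the sizing statement needs to be redone: the same formula with m = 1 gives 52 before any credit for the covariate, while 20 per group with the covariate at correlation 0.5 gave power 0.81 in the simulation above.

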Saline joint lavage represents a potentially simple, low-risk and minimal-cost intervention which has not been previously studied for this purpose in human subjects. Open joint lavage at the time of definitive surgical fixation is within the standard of care, but typically occurs greater than 10 days after injury by which time cartilage degradation has already begun. Early, saline lavage during initial presentation to the clinic or emergency department may theoretically alter the progression of the intra-articular inflammatory response by evacuating the bulk of the developing synovial-fluid fracture hematoma.

The vast majority of ankle fractures present to the ER or urgent care within a day of fracture. Moreover, a large subset of these fractures require reduction (fracture setting) that is painful. It is our standard of care to perform an intra-articular lidocaine injection before reduction. We will take advantage of this standard of care needle insertion to the fractured ankle to perform saline joint lavage to diminish this early inflammatory burden.

Design & Procedures

This is a prospective randomized control trial which will be performed exclusively at Duke University Hospital (DUH). We plan to enroll 60 patients with the hopes to have 40 evaluable subjects.

After informed consent is obtained, subjects will be randomized into one of two groups as listed below.

Group 1: intra-articular saline lavage (n=30)

Group 2: no intra-articular saline lavage (n=30)

Randomization will occur by the opening of pre-prepared envelopes which will be stored in the orthopaedic resident office (HAFS Building, Room 1661). Envelopes will be labeled #1-#60. Thirty envelopes will contain a note card labeled "Group 1" and Thirty envelopes will contain a note card labeled "Group 2". Envelopes will be pre-prepared by key study personnel not involved in the consent or randomization process.

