After the initial aspiration +/- lavage and stabilization of the ankle joint, subjects will undergo a period of soft tissue rest to allow for the resolution of soft tissue swelling. This is standard of care in the treatment of periarticular lower extremity fractures. Subjects will then undergo surgical fixation when it is deemed appropriate by the Orthopaedic Trauma team, independent of this study. At the time of surgery, after tourniquet inflation, all subjects will again undergo intra-articular aspiration of the injured ankle joint. This will be performed using a 16-gauge needle attached to a 10cc syringe via a standard anteromedial arthroscopy portal approach. The aspirate will be immediately aliquoted, transported to [name] lab (LSRC building B331) and stored at -80 degrees Celsius for batch analysis.

Selection of Subjects

Adult subjects (over 18 years of age) presenting to the DUH Emergency Department with an intra-articular fracture of the ankle joint between 0-48 hours from the time of injury will be eligible for inclusion. Intra articular fracture (IAF) is defined as any fracture of the fibula or tibia in which the fracture line(s) exit into the cartilage surface of the ankle joint. Exclusion criteria include: 1) age <18yo, 2) open fracture, 3) subjects presenting >48 hours from the time of injury, 4) nonoperatively treated fractures.

Subject Recruitment and Compensation

Upon evaluation by the orthopaedic surgery team in the Duke University Hospital Emergency Department, subject eligibility will be confirmed and the study will be introduced to the subject by their treating physician. Key personnel with role of "Collaborator" will review the study in detail with the subject. Paper consent forms will be signed and stored in a key-locked file cabinet within the study coordinators office (Duke Orthopaedics Arrington, 3rd Floor, Room 3262).

We plan to enroll 60 subjects to capture 40 participants as determined by our power analysis which is detailed below. All patients who meet the above inclusion criteria will be eligible for the study. In this way, enrollment will be equitable across all demographic groups.

Risk/Benefit Assessment

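### The primary RM-ANCOVA and its sample size assume two aspirates after baseline, but the procedures collect one, at surgery; the model and its power basis need restating.

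*Combined protocol and SAP*

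**What the plan says.** **Statistical sections.** Sample Size Estimate bases the between-group comparison on an RM-ANCOVA with "three dedicated time points ([1.] baseline, [2.] in the OR after anesthesia is induced (generally within 24 hours of lavage"; the third point is 1 to 2 weeks after injury. It adds: "Baseline cytokines and Matrix Metalloproteinase levels will be used as a covariate control". The calculation is described as "With an expected 80% power, 2 time intervals*, 1 control interval, two independent groups, and a standard error of probability of 0.05" and gives a minimum of 40 patients. Footnotes give 98 for a medium effect and 36 for three time intervals. Statistical Analyses says: "The primary outcome measure will be cytokines and Matrix Metalloproteinase levels measured at two distinct time points after injury".

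**Procedures.** Design & Procedures describes two aspirations. The first is in the emergency department (ED), before any lavage. The second follows a period of soft tissue rest: "At the time of surgery, after tourniquet inflation, all subjects will again undergo intra-articular aspiration of the injured ankle joint". The date of surgery is set clinically, independent of the study. Data & Safety Monitoring says of the subjects that "their involvement ends with their ankle joint aspiration at the time of surgery" and that no later contact is needed.

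**Timing elsewhere.** Background & Significance says that open lavage at definitive fixation "typically occurs greater than 10 days after injury".

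**The concern.** If baseline is the covariate, the repeated outcome has to come from the two later samples. The procedures yield only one later sample per patient. That sample might be the early OR point or the 1-to-2-week point, but it cannot be both for the same patient, and the sections disagree on which it usually is.

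Two things are at stake. First, the primary test is not defined for the data that will exist, so someone would have to choose the model after the data are in. One possible choice, counting the ED sample as one of the two outcome levels, changes what is estimated. Second, N = 40 was justified by a calculation that credits each patient with two post-baseline measurements.

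**Working it through.** **1. Count the samples.**

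| Section | Baseline | After baseline |
|---|---|---|
| Sample Size Estimate | 1 (covariate) | 2: OR, generally within 24 hours of lavage; 1 to 2 weeks after injury |
| Design & Procedures | 1 (ED, before lavage) | 1: at surgery, after soft tissue rest |
| Data & Safety Monitoring | not stated | none after surgery |

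No section schedules a third aspirate.

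**2. Reproduce the plan's figures.** The test is the between-groups F test for repeated measures, with N patients in two groups, m repeated measurements, correlation ρ between them and alpha 0.05:

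λ = N·m·f² / (1 + (m − 1)ρ), with 1 and N − 2 degrees of freedom.

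From the documents: 80% power, alpha 0.05, two groups, effect 0.40, two intervals plus one control interval. Assumed, because the documents do not say: 0.40 is read as Cohen's f (0.25 for the medium effect), and ρ = 0.5.

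- f = 0.40, m = 2: λ = 40 × 2 × 0.16 / 1.5 = 8.53; power 81.2%; smallest even N is 40. The plan says 40.
- f = 0.25, m = 2: λ = 98 × 2 × 0.0625 / 1.5 = 8.17; N = 98. The plan says 98.
- f = 0.40, m = 3: λ = 36 × 3 × 0.16 / 2 = 8.64; N = 36. The plan says 36.

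All three match, so N = 40 belongs to two repeated measurements in addition to baseline. The result depends on ρ: for f = 0.40 and m = 2, N is 28, 34, 40, 44 and 50 at ρ = 0, 0.3, 0.5, 0.7 and 0.9. The reading as Cohen's f also matters. The plan labels 0.40 as a partial squared measure, but a true partial eta squared of 0.40 gives f = √(0.4/0.6) = 0.82 and N = 12, not 40.

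**3. Same test with the one post-baseline value collected (m = 1).** λ = 40 × 0.16 = 6.4 with 1 and 38 degrees of freedom: power 69%. For 80% power N = 52 (λ = 52 × 0.16 = 8.32). This takes no credit for the covariate.

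**4. ANCOVA of the surgical value on group and baseline.** λ = N·f² / (1 − r²), with 1 and N − 3 degrees of freedom, f on the unadjusted scale and r the baseline-surgery correlation (assumed; the documents give none).

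| r | λ at N = 40 | Power at N = 40 | N for 80% |
|---|---|---|---|
| 0 | 6.40 | 69% | 52 |
| 0.3 | 6.4/0.91 = 7.03 | 73% | 48 |
| 0.5 | 6.4/0.75 = 8.53 | 81% | 40 |
| 0.7 | 6.4/0.51 = 12.55 | 93% | 28 |

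**5. If the ED value B is counted as an outcome level alongside the surgical value S.** Let S = a + δ·group + β·B + e. Then (B + S)/2 = a/2 + (δ/2)·group + ((1 + β)/2)·B + e/2. The group coefficient is δ/2 and its standard error is also halved, so the t statistic is that of the ANCOVA in step 4. The reported group difference is half the difference at surgery.

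**The case against.** The best defence is that little is lost in practice. With one post-baseline value the specified model reduces to an ordinary baseline-adjusted ANCOVA, which is a sound analysis, and at a correlation of 0.5 it needs 40 patients, the planned number. This stands. A reader might infer that the primary analysis is impossible or the trial unanalysable; the documents do not support that. What remains is that the plan does not specify the reduced model, and the agreement at N = 40 is a coincidence of r = 0.5, since the plan reached 40 by counting two later measurements.

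A second defence is that the two time points after injury in Statistical Analyses could mean the ED and surgical samples, both of which follow the injury. That reading conflicts with Sample Size Estimate, which lists baseline separately from two later points and makes it the covariate. A reader might go further and infer that averaging in the pre-lavage value would ruin power. That holds only for a model without the baseline covariate. The plan states the covariate, and step 5 shows that the test is then unchanged. The harm is a halved estimate.

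A reader might also fear that the planned chained-equations imputation would be used to create the missing time point. The plan mentions imputation in connection with drop-outs, and nothing suggests this wider use. It could not supply a time point observed in nobody.

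Finally, the documents do not show which section is out of date. A third aspirate may have been intended and left out of the procedures, so the repair cannot presume that the statistical text is the part in error.

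**Conclusion.** The point holds. The statistical sections require two post-baseline aspirates, the procedures supply one, and the sections disagree on its timing. The repeated-measures factor therefore does not exist in the data to be collected, and the stated basis for N = 40 does not apply to them.

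The size of the power consequence depends on a correlation that the documents do not give. Against a planned 80%, power at N = 40 is 69% with no covariate gain and 73% to 93% for correlations of 0.3 to 0.7. So 40 is not shown to be too few; it is unjustified as it stands. These figures assume f = 0.40 at the surgical aspirate. The plan expects the effect mainly at its second time point, the OR sample, so the unresolved timing also bears on whether 0.40 suits the sample actually taken.

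The contradiction in the text is certain. The power figures are conditional on the assumptions shown.

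**What to change.** 1. Reconcile Background & Significance, Design & Procedures, Sample Size Estimate, Statistical Analyses and Data & Safety Monitoring on how many aspirates each patient has and when.
2. For the procedures as written, replace the RM-ANCOVA in both statistical sections with an ANCOVA of the surgical-aspirate level on randomised group and pre-lavage level. Baseline enters as covariate only, never as an outcome level.
3. Name the adjusted group difference at surgery as the primary contrast. This is the comparison at fixation that the hypothesis in Purpose of the Study asks for.
4. Restate the power for 40 evaluable patients on that model, giving the assumed baseline-surgery correlation and a range, stating that 0.40 is Cohen's f if that is what was meant, and saying which time point it refers to.

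If the procedures stand, the cost is a rewrite of the two statistical sections and a new power calculation, with no change for patients. If reconciliation shows that a second post-baseline aspirate was intended, the procedures and the statement on when involvement ends would have to be corrected instead, and the cost would be larger.

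### The 80% power at N = 40 was calculated for two post-lavage measurements; for the one surgical aspirate in the procedures it holds only under two conditions that the plan does not state

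*Combined protocol and SAP*

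**What the plan says.** **Power calculation.** The Sample Size Estimate lists a baseline and two later time points, the later two being "in the OR after anesthesia is induced (generally within 24 hours of lavage), and [3] 1 to 2 weeks post-injury". The effect size is 0.40, described as a "large effect*, primarily occurring at the second time" point. The remaining inputs are "With an expected 80% power, 2 time intervals*, 1 control interval, two independent groups" and "a standard error of probability of 0.05". The result is "we estimated the need for a minimum sample size of 40 for statistical significance (~20 per group". Baseline levels are to be a covariate, but no correlation with later levels is given. Two footnotes below the Statistical Analyses section give alternative sample sizes: "Medium effect size required a sample size of 98", and 36 for three time intervals.

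**Analysis.** The Statistical Analyses section takes levels at two time points after injury as the primary outcome. It analyses them by RM-ANCOVA, with baseline as the covariate and more than one outcome time point.

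**Sampling.** Design & Procedures describes an aspirate in the emergency department before lavage or no lavage, a period of soft tissue rest, and one further aspirate in the operating room at surgical fixation. Data & Safety Monitoring says that participation ends with that surgical aspirate. Background & Significance says that joint lavage at definitive fixation "typically occurs greater than 10 days after injury".

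**The concern.** The calculation and the procedures describe different designs in two respects.

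- **Number of samples.** The calculation relies on two post-lavage measurements. The procedures provide one.
- **Timing.** The calculation expects the effect mainly at an operating-room sample about a day after lavage. The one sample in the procedures is also taken in the operating room, but if fixation follows the timing in the Background, it falls at about the plan's third time point, where the plan itself expects less effect.

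The section on recruitment bases enrolment on this power analysis. If the stated 80% is quoted for the trial as run, a null result could be taken as evidence that lavage does not work, when the chance of detecting the effect actually present at surgery may have been well below 80%.

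**Working it through.** **1. Inputs.** From the documents: power 80%, alpha 0.05 (a one-degree-of-freedom F test, so two-sided), equal groups, effect size 0.40, two time intervals, 40 evaluable patients. Not in the documents, so assumed: the correlation between repeated measurements and the correlation between baseline and surgery.

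**2. Reproducing the plan's figures.** For a between-group test on the mean of m repeated measurements with common correlation ρ:

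λ = N f² m / [1 + (m − 1)ρ], with 1 and N − 2 degrees of freedom.

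With ρ = 0.5 and N in steps of 2:

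| f | m | N | λ | Power | Plan's N |
|---|---|---|---|---|---|
| 0.40 | 2 | 40 | 40 × 0.16 × 2 / 1.5 = 8.53 | 81.2% | 40 |
| 0.25 | 2 | 98 | 98 × 0.0625 × 2 / 1.5 = 8.17 | 80.8% | 98 |
| 0.40 | 3 | 36 | 36 × 0.16 × 3 / 2 = 8.64 | 81.5% | 36 |

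N = 38 in the first row gives 79.1%. One model with one assumed correlation returns all three stated figures. It treats 0.40 as Cohen's f (d = 2f = 0.8) at full size on the two-measurement mean, and has no covariate term.

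The plan's label for the effect size is a separate slip. Read as partial eta squared, 0.40 would mean f = √(0.40/0.60) = 0.816 and N = 12, which is not what the plan reports.

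**3. Power for the sampling in the procedures.** One surgical aspirate, adjusted for baseline with correlation r:

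λ = N f² / (1 − r²), with 1 and N − 3 degrees of freedom.

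At N = 40 and f = 0.40, so N f² = 6.4:

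| r | λ | Power | d detectable with 80% power |
|---|---|---|---|
| 0 | 6.40 | 69% | 0.91 |
| 0.3 | 6.4 / 0.91 = 7.03 | 73% | 0.87 |
| 0.5 | 6.4 / 0.75 = 8.53 | 81% | 0.79 |

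Power crosses 80% at r of about 0.48. With no covariate, power is 69% and N = 52 would be needed.

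**4. If the effect has partly faded by surgery.** The plan gives no effect size for that time, so the fractions are assumptions.

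- Three-quarters remaining (f = 0.30, N f² = 3.6): power 46% at r = 0 and 57% at r = 0.5.
- Half remaining (f = 0.20, N f² = 1.6): power 23% at r = 0 and 30% at r = 0.5.

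**5. The plan's own medium effect.** With f = 0.25 (N f² = 2.5), the single-aspirate ANCOVA at N = 40 has 34% power at r = 0 and 43% at r = 0.5.

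**The case against.** The strongest reply is that the sample size survives the change of design. With a baseline correlation of 0.5, the single-aspirate ANCOVA has the same non-centrality as the plan's model, because 2/1.5 = 1/0.75. It gives N = 40 for f = 0.40 and N = 98 for f = 0.25. This is correct, and it rules out a stronger conclusion that a reader might draw: that the trial lacks 80% power. The documents do not support that, since they give neither the correlation nor the effect expected at surgery. Only the figure of 36 points specifically to the repeated-measures formula.

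Two other strong readings also fail.

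- A reader might infer that the effect was assigned to an aspirate that is never taken. The second time point is labelled as an operating-room sample, and an operating-room sample is taken from all subjects. The conflict lies in its timing and in the number of samples. The figure of more than 10 days describes usual practice, and the treating team decides when to operate.
- A reader might infer that averaging over two visits dilutes an effect present mainly at one of them. That needs two post-lavage visits. With one aspirate nothing is averaged, so this argument cannot be added to the one made here.

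The plan also discloses that a medium effect would need 98 patients, so low power for such an effect is not concealed. Enrolment of 60 would help if all were analysable (86% at f = 0.40 without the covariate), but the protocol expects 40 evaluable.

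What remains is that the 80% is stated without conditions, for a set of measurements that the procedures do not provide.

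**Conclusion.** The concern holds as a mismatch between the power statement and the procedures. The plan's arithmetic is correct for its own model, which takes credit for two post-lavage measurements with the full f = 0.40 on their mean.

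For the single surgical aspirate, the stated 80% needs two things: the full d = 0.8 present at surgery, and a baseline-surgery correlation of about 0.48 or more. The plan states neither, and placing the effect mainly at about 24 hours counts against the first. With the full effect, the shortfall is modest at low correlation (69% to 73% at 0 to 0.3) and disappears at 0.5. If the effect has faded by surgery, the shortfall is large.

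These figures rest on the plan's assumption of normality, 20 evaluable patients per group, a two-sided 0.05 test and the assumed correlations.

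**What to change.** 1. Reconcile the number and timing of post-lavage aspirates across Background & Significance, Design & Procedures, Sample Size Estimate, Statistical Analyses, and Data & Safety Monitoring.
2. If one surgical aspirate is what is collected, replace the two-interval calculation and the two-time-point RM-ANCOVA with an ANCOVA of the surgical level on group and baseline level. Remove the statement that the effect lies mainly at the second of three time points.
3. State that 40 evaluable patients give 80% power for d of about 0.79, 0.87 or 0.91 at a baseline-surgery correlation of 0.5, 0.3 or 0, and give the reason for expecting an effect of that size at surgery.
4. State that a null result does not exclude moderate effects.

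The cost is a rewritten sample-size and analysis paragraph with a slightly less favourable, conditional power statement. No change in N is needed.
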